**Table 6. Non-reportable medical occurrences associated with the index implant procedure**

Event	Timeframe (hours) from the Index Procedure
Short transient episode of arrhythmia (including ventricular fibrillation) during index procedure	0
Confusion, anxiety and/or disorientation (other than TIA/stroke) starting within 48 hours with or without medical intervention	120 (5 days)
Temporary change in mental status (other than TIA/stroke) not requiring additional medical interventions or new medical assessments (eg, CT)	72
Dizziness and/or lightheadedness with or without treatment	24
Headache with or without treatment	72
Sleep problems or insomnia with or without treatment	120 (5 days)
Mild dyspnea or cough with or without treatment	72
Oxygen supply after extubation/“forced breathing therapy”	48
Diarrhea with or without treatment	48
Obstipation/Constipation with or without treatment	72
Anesthesia-related nausea and/or vomiting with or without treatment	24
Low-grade fever (<101.3°F or <38.5°C) without confirmed infection	48
Low body temperature	6
Pain (eg, back, shoulder) related to laying on the procedure table with or without treatment	72
Incisional pain (pain at access site) with or without standard treatment and patient not returning to clinic to have additional treatment	No time limit
Pain in throat and/or trachea due to intubation	72
Mild to moderate bruising or ecchymosis	168 (7 days)
Atelectasis/Pleural Effusion not requiring punctuation	168 (7 days)
Edema resulting in weight increase up to 4 kg/9lbs from baseline	168 (7 days)

For all observed AEs, investigators should assess and document the following information on the Adverse Event eCRF:

- Date of onset or first observation
- Date of site’s first awareness
- AE code number
- Description of the event
- Seriousness of the event
- Causal relationship of the event to the TAV or surgical valve
- Causal relationship of the event to the DCS and/or LS

- Causal relationship of the event to the TAVR implant procedure
- Treatment required
- Outcome or status of the event
- Date of resolution
- For all deaths, investigators should assess and document the following information on the Adverse Event eCRF
  - Date of death
  - Primary death category
  - Causal relationship of the event to the TAV or surgical valve
  - Causal relationship of the event to the DCS and/or LS
  - Causal relationship of the event to the implant procedure

In addition, for all endpoint-related adverse events and deaths, sites should submit relevant, de-identified source documents to Medtronic for the Clinical Events Committee (CEC) members to use in their adjudication of the event. The CEC may request source documentation on additional events at their discretion and according to the CEC Charter.

Definitions of safety endpoints, the AE code list, and guidelines for accessing causal relationships are provided in APPENDIX V: DEFINITIONS: SAFETY ENDPOINTS AND EFFICACY EVENTS

### 10.2.2. Anticipated Adverse Events

Adverse events that are anticipated for subjects participating in this study are provided in Section 9.1, Risks.

### 10.2.3. Adverse Event Reporting Requirements for Clinical Sites

Adverse events and device deficiencies that occur during this study are required to be reported to Medtronic via the AE or device deficiency eCRF, as soon as possible after the event occurs, but no later than the timeframes listed in Table 7 or local requirements, whichever is more stringent.

**Table 7. Required timeframes for adverse event reporting to Medtronic**

Event Type	Timeframe for Reporting
Adverse Event (AE)	No later than 10 working days of the investigator's/site's first knowledge of the event
Serious Adverse Event (SAE)	Immediately, but no later than 72 hours of the investigator's/site's first knowledge of the event
Adverse Device Effect (ADE) or Device Related Adverse Event	Immediately, but no later than 72 hours of the investigator's/site's first knowledge of the event
Serious Adverse Device Effect (SADE)	Immediately, but no later than 72 hours of the investigator's/site's first knowledge of the event
Unanticipated Adverse Device Effect (UADE)	Immediately, but no later than 72 hours of the investigator's/site's first knowledge of the event

Event Type	Timeframe for Reporting
Device Deficiency	No later than 72 hours of the investigator's/site's first knowledge of the event

In addition, Investigators are obligated to report adverse events in accordance with the requirements of their reviewing IRB/EC and local regulations.

The Sponsor is obligated to report adverse events and device deficiencies that occur during this study to the Regulatory Authorities and IRB/EC as per local requirements. The applicable timeframes are described in the Safety Plan associated with this study.

#### **10.2.4. Documentation and Reporting of Device Deficiencies**

Device deficiency information will be collected throughout the study and reported to Medtronic. Device deficiencies that led to an AE are reported on the AE eCRF. Device deficiencies that did not lead to an AE should be reported on a Device Deficiency eCRF (one for each device deficiency).

#### **10.2.5. Emergency Contact Details for Reporting SAE, SADE, UADE, and Device Deficiencies**

Investigators should contact their Medtronic clinical study manager or site manager if they have any questions regarding reportable AEs. Medtronic will provide and maintain a listing of current contact details for each site.

## **11. Data Review Committees**

---

### **11.1. Clinical Events Committee**

A Clinical Events Committee (CEC) will provide independent medical review and adjudication of adverse event data used in the safety assessment of the investigational device. The CEC will adjudicate, at a minimum, all deaths and safety endpoint-related adverse events reported by the investigators. The analysis of the study safety data will be based on CEC adjudicated events. Safety endpoint definitions are provided in APPENDIX V: DEFINITIONS: SAFETY ENDPOINTS AND EFFICACY EVENTS.

The CEC members will be free from bias towards the study and will be independent from both the study and investigators and Medtronic. The committee will consist of at least 3 independent experts (non-Medtronic employed physicians) with expertise relevant to the study. This will include experience in the areas of:

- Cardiac surgery
- Interventional cardiology
- Neurology
- Electrophysiology

A CEC charter will be established that describes the Committee roles, responsibilities, and processes.

## **11.2. Data Safety Monitoring Board**

A Data Safety Monitoring Board (DSMB) will assess interim study data and provide recommendations to Medtronic regarding study conduct, should they identify any issues that may affect the safety of the study subjects. DSMB members will be free from bias towards the study and will be independent from both the study and investigators and Medtronic.

The DSMB will consist of a minimum of 3 members who will have experience in the areas of:

- 1) a cardiologist with expertise in the management of aortic stenosis
- 2) a cardiothoracic surgeon with expertise in aortic valve replacement
- 3) a statistician

A DSMB charter will be established that describes the Committee roles, responsibilities, and processes. The DSMB will meet (via teleconference or in person) prior to the first subject enrollment to establish procedures for safety data review, chairman appointment, and guidelines for study recommendations. The DSMB will meet on a periodic basis to perform a comprehensive data review, including at a minimum, all SAEs and deaths, and will meet more frequently when needed. Safety-related endpoints may also be reviewed at these meetings. DSMB meetings may consist of both open and closed sessions. Medtronic personnel may facilitate the DSMB meeting but will not have voting privileges.

Following each meeting, the DSMB will report to Medtronic in writing and may recommend changes in the conduct of the study. The DSMB recommendations may include recommendations on study status such as continuing the study without modifications, continuing the study with modifications, stopping or suspending enrollment, or recommendations regarding study conduct including recommendations around enrollment or protocol deviations.

In the case of UADEs, if Medtronic and the DSMB determine that the event presents an unreasonable risk to the participating subjects, Medtronic must terminate the clinical study within 5 working days after making that determination and no later than 15 working days after Medtronic first receives notice of the effect. All clinical sites will be notified of this action.

The DSMB may call additional meetings if, at any time, there is concern about any aspect of the study. All data presented at the meetings will be considered confidential.

## 12. Statistical Design and Methods

### 12.1. Sample Size and Results Reporting

This study will involve 150 subjects with an attempted implant with the Medtronic TAVR system. The primary analysis will be performed when 150 consecutive subjects with an attempted implant have had the chance to complete 30-day follow-up. Results from the primary analysis will be used for regulatory submissions. Another analysis may be performed when all 150 subjects with an attempted implant have completed 1 year follow-up. The final analysis will be performed with all implanted subjects have completed 10-year follow-up.

This is not a hypothesis-driven study, therefore the sample size of 150 for the analysis was not determined by statistical sample size methods. However, a sample size of 150 subjects is adequate for a descriptive assessment of the procedural safety and efficacy of the Medtronic TAVR system in subjects with bicuspid aortic valves. The results from the primary endpoints of the Low Risk bicuspid study cohort will be compared to the procedural safety and efficacy results from the TAVR arm of the Low Risk Trial randomized cohort.

### 12.2. Enrolled Subjects and Analysis Sets

#### Enrolled Subjects

All subjects with severe aortic stenosis and bicuspid anatomy who provide an informed consent will be considered screened and enrolled and all available data will be entered into the Electronic Data Capture (EDC) system.

#### Analysis Sets

There are two different analysis sets that are defined for this study. The primary analysis will be the “attempted implant” analysis. Analysis sets used for each objective are defined under the corresponding objective section. The analysis subsets are defined as follows:

**Attempted implant set:** The attempted implant set consists of all enrolled subjects with an attempted implant procedure, defined as when the subject is brought into the procedure room and any of the following have occurred: anesthesia administered, vascular line placed, TEE placed or any monitoring line placed. Subjects will be analyzed according to their first attempted procedure (TAVR). Day 0 is date of first attempted procedure.

**Implanted set:** The implanted set consists of all the attempted implant subjects who are actually implanted with the TAV. Day 0 is date of first attempted procedure.

### **12.3. Description of Baseline Variables**

Baseline demographic and clinical variables will be summarized for as attempted implant analysis set. All continuous variables will be summarized with means, medians, standard deviations, minimums, and maximums. Categorical variables will be summarized with frequencies and percentages.

### **12.4. Endpoint Analysis**

All endpoints are descriptive and no statistical hypothesis test will be performed.

### **12.5. Primary Safety Endpoint #1 – All-cause Mortality or Disabling Stroke Rate at 30 Days**

This endpoint will be analyzed for as attempted implant set. The Kaplan-Meier rate and a 95% two-sided confidence interval will be calculated.

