6.2. Sample Size

This study will involve 150 subjects with an attempted implant with the Medtronic TAVR system. The primary analysis will be performed when 150 consecutive subjects with an attempted implant have had the chance to complete 30-day follow-up.

This is not a hypothesis-driven study, therefore the sample size of 150 for the analysis was not determined by statistical sample size methods. However, a sample size of 150 subjects is adequate for a descriptive assessment of the procedural safety and efficacy of the Medtronic TAVR system in subjects with bicuspid aortic valves. Table 2 provides the level of precision with

the 95% confidence intervals around possible endpoint rates in bicuspid subjects at sample sizes of 150 subjects (assuming that when occurred, the endpoint rates in bicuspid subjects are similar to those in the historical data from tricuspid subjects). The rates provided are based on the weighted average from historical data presented in Table 1.

Table 2. Confidence intervals for sample sizes of 150 subjects.

Endpoint	Possible Rate in Bicuspid Subjects (n) ¹	Sample Size	95% Exact Binomial Confidence Interval
All-cause mortality or disabling stroke at 30 days	2.7% (4)	150	0.7%, 6.7%
Device success	94.7% (142)	150	89.8%, 97.7%

¹Rate values from the weighted average of the historical data are rounded up to correspond to the nearest whole number for subjects with an endpoint for sample sizes of 150; n denotes number of subjects with an endpoint.

7. Statistical Methods

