7.2. General Methodology

Descriptive statistics will be used to report study data. For continuous variables (eg. age), the mean, median, standard deviation, minimum, maximum and interquartile ranges (IQR) will be presented. For categorical variables, the number and percentage of subjects in the category of interest will be presented.

For time to event variables, Kaplan-Meier analyses of event rates at 30 days, 1 year and annually through end of study will be presented. For these analyses, the time points will correspond to 30 days, 365 days, 730 days, 1095 days, 1460 days, 1825 days, 2190 days, 2555 days, 2920 days, 3285 days and 3650 days post implantation respectively. At each time point with data, the product limit estimate of the event, the number of subjects at risk, the number of subjects with events, and the 95% confidence interval will be presented. For subjects without an event, the date of censoring will be the latest date of all follow-up visits, assessments, and events (including death).

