7.4. Handling of Missing, Unused, and Spurious Data and Dropouts

Every effort will be undertaken to minimize missing data. In time-to-event outcomes drop-outs will be censored at the time of discontinuation, consistent with the Kaplan-Meier approach.

Missing (accidentally, due to withdrawal, missing follow-up or loss to follow-up, etc.), unused and spurious data will remain identifiable in the database. Data from subjects that cannot be analyzed for a specific variable will be displayed as missing in the relevant summary tables. In this manner, all data for a specific variable are accounted for. Unless otherwise specified, no statistical techniques will be used to impute missing data. The number of subjects included in each analysis will be reported so that the reader can assess the potential impact of missing data.

In the case of partial dates, if only the month and year are known, the event or assessment will be analyzed as if it occurred on the 15th of that month. If only the year is known, the event or assessment will be analyzed as if it occurred on June 30th of that year. These resolutions of partial dates are subject to the restrictions that events must occur no earlier than the procedure date.

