7.9. Evaluation of Objectives

7.9.1. Primary Safety Endpoint

All-cause Mortality or Disabling Stroke Rate at 30 days.

Hypothesis/Decision criteria:

No specific hypotheses or pass/fail criteria have been set. The analysis will be descriptive and no statistical hypothesis test will be performed.

Endpoint Definition/Parameters to Be Estimated:

The endpoint is the KM event rate of all-cause mortality or disabling stroke at 30 days post procedure.

Data Collection and Analysis Method:

Data will be collected on event case report form. Death and stroke events will be adjudicated by the CEC. CEC adjudicated all-cause mortality or disabling stroke will be used in the analysis.

Analysis Dataset:

This objective will be analyzed for all attempted implant set.

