7.9.3. Additional Outcome Measures

1. All-cause mortality at one year, and annually through 10 years

Event rate estimates will be provided at 1 year and annually thereafter up to 10 years for the attempted implant set. The outcome is descriptive including Kaplan-Meier rates and no statistical hypothesis test is specified.

2. All stroke (disabling and non-disabling) at one year, and annually through 10 years

Event rate estimates will be provided at 1 year and annually thereafter up to 10 years for the attempted implant set. The outcome is descriptive including Kaplan-Meier rates and no statistical hypothesis test is specified.

3. New permanent pacemaker implantation at 30 days

Event rate estimates will be provided at 30 days for the attempted implant set. The outcome is descriptive including Kaplan-Meier rates and no statistical hypothesis test is specified.

4. Myocardial Infraction at 30 days

Event rate estimates will be provided at 30 days for the attempted implant set. The outcome is descriptive including Kaplan-Meier rates and no statistical hypothesis test is specified.

5. Life-threatening bleeding at 30 days, one year, and annually through 10 years

Event rate estimates will be provided at 30 days, 1 year and annually thereafter up to 10 years for the attempted implant set. The outcome is descriptive including Kaplan-Meier rates and no statistical hypothesis test is specified.

6. Prosthetic valve endocarditis at 30 days, one year, and annually through 10 years

Event rate estimates will be provided at 30 days, 1 year and annually thereafter up to 10 years for the attempted implant set. The outcome is descriptive including Kaplan-Meier rates and no statistical hypothesis test is specified.

7. Prosthetic valve thrombosis at 30 days, one year, and annually through 10 years

Event rate estimates will be provided at 30 days, 1 year and annually thereafter up to 10 years for the attempted implant set. The outcome is descriptive including Kaplan-Meier rates and no statistical hypothesis test is specified.

8. Valve-related dysfunction requiring repeat procedure at 30 days, one year, and annually through 10 years

Event rate estimates will be provided at 30 days, 1 year and annually thereafter up to 10 years for the attempted implant set. The outcome is descriptive including Kaplan-Meier rates and no statistical hypothesis test is specified.

9. Repeat hospitalization for ascending aorta disease at 30 days, one year, and annually through 10 years

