Level 1 validation (independent validation) will be used for the analysis datasets and the primary endpoints. Level 1 or 2 validation (peer review) will be used for additional analyses, data summaries, and listings.

9. References

NA

10. Statistical Appendices

There are no statistical appendices for this study.

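### Does the primary safety endpoint need a named Kaplan-Meier interval because SAP Table 2 shows an exact binomial one?

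*Protocol*

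**What the plan says.** Protocol 12.5 plans the primary safety analysis in one sentence on method: "The Kaplan-Meier rate and a 95% two-sided confidence interval will be calculated". SAP 7.9.1 defines the target: "The endpoint is the KM event rate of all-cause mortality or disabling stroke at 30 days post procedure". SAP 7.2 lists the output for every time-to-event variable: "the product limit estimate of the event, the number of subjects at risk, the number of subjects with events, and the 95% confidence interval". SAP 7.4 adds the censoring rule: "In time-to-event outcomes drop-outs will be censored at the time of discontinuation, consistent with the Kaplan-Meier approach".

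None of these sections names a variance estimator, a scale for the interval or a rule for zero events, and SAP section 10 closes off another source: "There are no statistical appendices for this study". The only interval method named in either document is in the precision table of SAP 6.2, whose column is headed "95% Exact Binomial Confidence Interval".

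Protocol 12.4 and SAP 7.9.1 make the endpoint descriptive, with no hypothesis test. SAP 7.9.1 adds that there is no pass/fail criterion.

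**The concern.** The stated precision of the study belongs to an interval that the analysis sections do not commit to. A Kaplan-Meier interval can be built in several ways, and with about four expected events in 150 they do not agree. The linear Greenwood interval puts its upper limit too low when events are rare, which for a safety endpoint is the wrong direction. At zero events the Greenwood standard error is zero: the linear interval shrinks to a point and the log-log interval cannot be computed.

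The setting adds weight. Of the primary analysis, Protocol 12.1 says: "Results from the primary analysis will be used for regulatory submissions". It also plans to set the primary results beside the TAVR arm of the Low Risk Trial. With no test planned, the interval is the only stated measure of uncertainty for primary safety. The same unnamed approach serves other 30-day outcomes in SAP 7.9.3, such as myocardial infarction: "Event rate estimates will be provided at 30 days for the attempted implant set". A method left open could in principle be chosen after the data are seen.

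**Working it through.** **Inputs.** n = 150 and 4 events (SAP Table 2). Historical 30-day rates from SAP Table 1: 4/394, 13/301, 1/60 and 2/60. Assumption, not in the documents: nobody is censored before day 30, so the Kaplan-Meier rate is x/n and the Greenwood standard error is √(S(1−S)/n), with S = 1 − x/n.

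**Table 2 reproduced.** The exact (Clopper-Pearson) interval for 4/150 is 0.73% to 6.69%, matching the printed 0.7% and 6.7%. The pooled historical rate is (4+13+1+2)/(394+301+60+60) = 20/815 = 2.45%. Then 150 × 0.0245 = 3.68, rounded up to 4 as the table's footnote says. The table is arithmetically correct.

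**Kaplan-Meier intervals at 4/150.** S = 146/150 = 0.97333; SE = √(0.97333 × 0.02667/150) = 0.01315.

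- Linear: 2.67% ± 1.96 × 1.315% = 0.09% to 5.24%.
- Log-log: w = 1.96 × SE/(S × |ln S|) = 1.96 × 0.01315/(0.97333 × 0.02703) = 0.980. The limits are 1 − S^exp(−w) = 1 − 0.97333^0.375 = 1.01% and 1 − S^exp(w) = 1 − 0.97333^2.664 = 6.95%.

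The log-log upper limit differs from the exact one by 6.95 − 6.69 = 0.26 points. The linear one differs by 6.69 − 5.24 = 1.45 points.

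**Zero events.** Linear gives 0% to 0%; log-log is undefined; the exact upper limit is 1 − 0.025^(1/150) = 2.43%.

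**Behaviour over the Table 1 rates.** P(0) = (1 − p)^150. Coverage is the sum of binomial probabilities, n = 150, over the outcomes whose interval contains p.

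| True rate p | P(0 events) | Linear coverage | Linear upper limit below p | Log-log coverage, given ≥1 event | Log-log with exact limit at zero | Exact coverage |
|---|---|---|---|---|---|---|
| 1.02% | 21.5% | 78.4% | 21.5% | 97.6% | 98.1% | 98.1% |
| 1.67% | 8.0% | 91.6% | 8.0% | 95.6% | 95.9% | 98.7% |
| 2.45% (pooled) | 2.4% | 88.1% | 11.5% | 96.7% | 94.3% | 96.4% |
| 3.33% | 0.6% | 87.5% | 12.0% | 97.0% | 96.4% | 98.2% |
| 4.32% | 0.1% | 88.6% | 10.8% | 97.0% | 96.9% | 97.6% |

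The unsatisfactory figures are in the two linear columns. The log-log form has trouble only in the P(0) column.

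**What the reader still has at zero events.** SAP 7.2 requires the number at risk and the number of events at each time point. From 0 events and 150 subjects the 2.43% limit follows in one step. If 5 subjects had been censored early without an event (assumed), using 145 gives 1 − 0.025^(1/145) = 2.51%, so censoring of that order barely moves it.

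**Pacemaker implantation.** Protocol 3.1 cites rates of 19% to 40% in bicuspid patients. At 19%, P(0) = 0.81^150, about 2 × 10⁻¹⁴. The zero-event question does not arise for that 30-day outcome.

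**The case for a change.** The strongest case for a change is that a SAP exists to settle such choices before the data are seen, and that settling this one is cheap. Low counts are realistic: the Table 1 cohorts had mean STS scores of 4.0 to 7.3, whereas this trial requires a predicted surgical mortality below 3%, so the rate could lie nearer 1% than 2.45%. If the linear form were used, its upper limit would fall below the true rate in 8% to 21.5% of trials against a nominal 2.5%, and that does not depend on zero events alone.

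The arithmetic stands, and so does the statement that the method is unnamed. The inference to a defective plan does not. The linear figures describe a choice that neither document makes. With log-log, the interval is close to Table 2 and has adequate coverage once an event occurs. At zero events the absence of a computable interval would be obvious in the output, and the exact limit is the natural entry. The beta product interval would also serve, since it equals the exact interval without censoring. Preferring it to log-log with an exact limit at zero is a choice between valid methods.

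Protocol 12.5 stays true under any two-sided 95% method. Editing it would invoke the amendment process of Protocol 14.6 without altering what is promised.

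**Conclusion.** No change to the plan is needed. The documents leave out a technical detail, but contain no wrong rule. Table 2 is correct and serves to describe the precision of 150 subjects; it differs from a log-log Kaplan-Meier interval by about 0.3 points at the upper limit for 4/150. The remaining gap is the zero-event case: probability 2.4% at the pooled historical rate, 21.5% at the lowest of the four study rates. In that case the required counts give an upper limit of about 2.4% directly. No success criterion, test or sample-size argument depends on the interval.

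This rests on three assumptions: little or no censoring before day 30, true rates within the range of SAP Table 1, and an analyst who uses an interval suited to rare events and states it in the report. If the linear form were used, the upper limit at 4/150 would be about 1.5 points below the exact one. That would be a fault of execution, visible from the reported event count and number at risk.
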